5.7 Criteria for Taking a Participant Off Study

Participants will be removed from study when any of the following criteria apply:

- Lost to follow-up
- Withdrawal of consent for data submission
- Death

The reason for taking a participant off study, and the date the participant was removed, must be documented in the case report form (CRF). In addition, the study team will ensure the participant's status is updated in OnCore in accordance with DF/HCC policy REGIST-OP-1.

6. DOSING DELAYS/DOSE MODIFICATIONS

For participants who are unable to tolerate the protocol-specified dosing schedule, dose adjustments are permitted in order to keep the participant on study drug. If administration of abemaciclib must be interrupted because of unacceptable toxicity, drug dosing will be interrupted or modified according to rules described in Table 6.3.

The descriptions and grading scales found in the revised NCI Common Terminology Criteria for Adverse Events (CTCAE) version 4.0 will be utilized for dose delays and dose modifications. A copy of the CTCAE version 4.0 can be downloaded from the CTEP website http://ctep.cancer.gov/protocolDevelopment/electronic applications/ctc.htm.

In the case of toxicity, appropriate medical treatment should be used (including anti-emetics, anti-diarrheals, etc.).

All adverse events experienced by participants will be collected from the time of the first dose of study treatment, through the study and until the 30 day post-study visit (see section 10). Participants continuing to experience toxicity at the end-of treatment visits may be contacted for additional assessments until the toxicity has resolved or is deemed irreversible.

All participants will be initially treated at Dose Level 0.

Table 6.0: Dose Levels

Dose Level	Dose of Abemaciclib
1*	200 mg every 12 hours
0 (starting dose)	150 mg every 12 hours
-1	100 mg every 12 hours
-2	50 mg every 12 hours

^{*}If a patient has not required dose reduction(s) due to toxicity, then the dose of Abemaciclib may be escalated at the start of Cycle 2 to 200 mg every 12 hours if the investigator determines that it is in the best interest of the patient.

6.1 Anticipated Toxicities

In order for an event to be expected (known correlation to study drug) for the purposes of adverse event reporting, the event must be included in this section.

- 6.1.1 A list of adverse events of all grades suspected to be abemaciclib treatment related according to review of Investigator's Brochure, organized by CTCAE v4.0 category, includes:
 - BLOOD & LYMPHATIC SYSTEM DISORDERS White blood cell decreased, Neutrophil count decreased, Platelet count decreased, Anemia
 - EYE DISORDERS Cataract
 - GASTROINTESTINAL Diarrhea, Nausea, Vomiting, Dry mouth, Stomatitis
 - GENERAL DISORDERS Fatigue
 - INFECTIONS & INFESTATIONS Upper respiratory infection, lung infection, pharyngitis, urinary tract infection, conjunctivitis, sinusitis, vaginal infection, sepsis
 - INVESTIGATIONS Creatinine increased, Weight loss, Aspartate aminotransferase increased, Alanine aminotransferase increased, GGT increased
 - METABOLISM & NUTRITION DISORDERS Anorexia
 - MUSCULOSKELETAL AND CONNECTIVE TISSUE DISORDERS Muscular weakness
 - NERVOUS SYSTEM DISORDERS Dysgeusia, Dizziness
 - RESPIRATORY, THORACIC & MEDIASTINAL DISORDERS Pneumonitis
 - SKIN AND SUBCUTANEOUS TISSUE DISORDERS Alopecia, Rash, Pruritis

• VASCULAR DISORDERS – Thromboembolic event

6.2 Dose Modifications/Delays

- 6.2.1 Table 6.3 should be adhered to for all toxicities considered at least possibly related to abemaciclib as noted below. If a participant experiences a toxicity unlikely or unrelated to treatment with abemaciclib but may still warrant a hold or reduction of study drug for safety, discussion and approval by Overall Principal Investigator and Study Sponsor, [name] [name] is recommended.
- 6.2.2 When treatment must be held pending resolution of toxicity to grade 1 or return to baseline, and the toxicity is a lab abnormality, in cases where participant had a pre-existing laboratory abnormality at baseline, the toxicity can be considered "resolved" from a hold perspective when it has resolved to within 1 grade of the baseline value. NOTE: For the purposes of data entry, values from screening assessments should be entered in as 'baseline' values. However, true "baseline values" for the purpose of dose modifications on study, etc. will be considered the last assessments/tests performed prior to initiation of study therapy.
 - EXCEPTION: In instances where the value within 1 grade of the baseline value would still require a hold, continue to hold until resolution of toxicity to grade 1 or return to baseline.
- 6.2.3 Participants who experience an adverse event that requires a treatment delay or dose reduction should be monitored with appropriate laboratory testing or other clinical evaluation at least weekly until resolution
- 6.2.4 Following a dose delay which resumes mid cycle, day 1 procedures not associated with the adverse event do not need to be repeated.
- 6.2.5 No more than 2 levels of dose reduction are permitted in this study. Participants cannot be treated below dose level -2. If a participant whose abemaciclib dose has been reduced by 2 dose levels requires another dose reduction, treatment on study must be stopped unless the participant has benefited from the study, in which case the investigator will contact the overall Principal Investigator, [name] [name], to determine if the participant will remain in the study.
- 6.2.6 A treatment delay of up to 28 days is permitted. If the toxicity has not resolved after a 4-week delay, the participant must be removed from study treatment unless the participant has benefited from the study, in which case the investigator may contact the Overall Principal Investigator, [name] [name], to determine if the participant will remain in the study.
- 6.2.7 Dose re-escalation is never permitted in this study.

- 6.2.8 Cycle length will be 4 weeks (28 days), even if treatment is held for toxicity. There is no stopping in counting cycles/days for those periods where a subject's drug is withheld. All study evaluations and treatments should continue as if study treatment is not being held.
- 6.2.9 If study drug is held across a time point which requires collection of a research blood sample, please contact the Sponsor Coordinating Center or Overall PI ([name] [name]) to confirm whether or not the sample should be collected or if the drug hold will negate the value of collection of the sample in question. If you anticipate the occurrence of such a scenario, please contact the Sponsor Coordinating Center as soon as possible in order to establish a plan prior to the time point in question.
- 6.2.10 Participants whose treatment is interrupted or permanently discontinued due to an adverse event or clinically significant laboratory value, must be followed as outlined in Table 6.3, at least once a week for 4 weeks, and subsequently at 4-week intervals, until resolution or stabilization of the event, whichever comes first. All participants must be followed for adverse events and serious adverse events for 30 days following the last dose of abemaciclib. All SAEs must be reported as detailed in Section 7.4.

Table 6.3: Criteria for dose-modification and re-initiation of abemaciclib treatment

Table 6.3 should be adhered to for all toxicities considered at least possibly related to abemaciclib as noted below. If a participant experiences a toxicity unlikely or unrelated to treatment with abemaciclib but may still warrant a hold or reduction of study drug for safety, discussion and written approval by Overall Principal Investigator and Study Sponsor, [name] [name] is recommended.

Toxicity Actions

(organized per CTCAE v 4.0)

Investigations (for hyperglycemia, see metabolism disorders)

Unless otherwise specified, during duration of toxicity.

General Guidance for Hepatic Monitoring

Details for hepatic monitoring depend upon the severity and persistence of observed laboratory test abnormalities. If a study patient experiences elevated ALT 5×ULN and elevated TBL 2×ULN, or ALT 8×ULN, liver tests, including ALT, AST, TBL, direct bilirubin, gamma glutamyl transferase (GGT), and creatine phosphokinase (CPK), should be repeated within 3 to 5 days to confirm the abnormality and to determine if it is increasing or decreasing. If the abnormality persists or worsens, clinical and laboratory monitoring should be initiated by the investigator, based on the hepatic monitoring tests below.

Hepatic Hematology Haptoglobin

Hemoglobin

Hematocrit RBC WBC

Neutrophils, segmented and bands

Lymphocytes
Monocytes
Eosinophils
Basophils

Platelets

Hepatic Chemistry

Total bilirubin
Direct bilirubin

Alkaline phosphatase

ALT AST

GGT CPK

Hepatic CoagulationProthrombin Time
Prothrombin Time, INR

Hepatic Serologiesa

Hepatitis A antibody, total Hepatitis A antibody, IgM Hepatitis B surface antigen Hepatitis B surface antibody Hepatitis B Core antibody Hepatitis C antibody Hepatitis E antibody, IgG Hepatitis E antibody, IgM

Anti-nuclear antibody
Anti-actin antibody

Anti-smooth muscle antibody

Abbreviations: ALT = alanine aminotransferase; AST = aspartate aminotransferase; CPK = creatine phosphokinase; GGT = gamma-glutamyl transferase; Ig = immunoglobulin; INR = international normalized ratio; RBC = red blood cells; WBC = white blood cells.

a Reflex/confirmation dependent on regulatory requirements and/or testing availability.

ALT/SGPT or AST/SGOT

- Grade 2 (>3.0- 5.0 x ULN) WITHOUT increase in total bilirubin above 2 x ULN

First Occurrence:

Interrupt until resolution to ≤ grade 1, then

- If resolution to grade ≤1 in ≤ 7 days, resume ABEMACICLIB at the current dose level
- If resolution to ≤ grade 1 takes > 7 days, resume ABEMACICLIB at one lower dose level

Second/Third Occurrence:

Interrupt until resolution to ≤ grade 1, then resume ABEMACICLIB at one lower dose level

ALT/SGPT or AST/SGOT - Grade 3 (> 5.0 - 20.0 x ULN)	First Occurrence: Interrupt until resolution to ≤ grade 1, then • If resolution to grade ≤1 in ≤ 7 days, resume ABEMACICLIB at the current dose level • If resolution to ≤ grade 1 takes > 7 days, resume ABEMACICLIB at one lower dose level Once resolved to ≤ grade 1, monitor liver function tests every other week or more frequently if clinically indicated until the end of treatment with study medication. Second/Third Occurrence: Interrupt until resolution to ≤ grade 1, then resume ABEMACICLIB at one lower dose level Once resolved to ≤ grade 1, monitor liver function tests every other week or more frequently if clinically indicated until the end of treatment with study medication.
ALT/SGPT or AST/SGOT - Grade 3 (> 5.0 - 20.0 x ULN) WITH increase in total bilirubin above 2 x ULN in the absence of cholestasis	Discontinue abemaciclib.
ALT/SGPT or AST/SGOT - Grade 4 (>20.0 x ULN)	Discontinue abemaciclib.

General Guidance for Increases in Serum Creatinine and Assessment of Renal Insufficiency

Abemaciclib has been shown to increase serum creatinine due to inhibition of renal tubular transporters without affecting glomerular function (as measured by iohexol clearance). In clinical studies, increases in serum creatinine occurred within the first month of abemaciclib dosing, remained elevated but stable through the treatment period, were reversible upon treatment discontinuation, and were not accompanied by changes in markers of renal function, such as blood urea nitrogen (BUN), cystatin C, or calculated glomerular filtration rate based on cystatin C.

Creatinine - Grade 2 (>1.5 - 3 x ULN)	Maintain treatment with ABEMACICLIB
Creatinine - Grade 3 (> 3.0 - 6.0 x ULN) if believed deterioration of renal function is suspected (as evidenced by changes in other markers of renal function, such as BUN, cystatin C, or calculated GFR based on cystatin C).	Interrupt treatment until resolution to ≤ grade 1 or returned to baseline, treatment may resume at the same dose level or a 1 dose level decrease, at the investigator's discretion. Continuation of ABEMACICLIB is permitted upon recovery to stable Grade 2 if the investigator and overall principal investigator ([name] [name]) agree that the event is not considered clinically significant.
Creatinine - Grade 4 (> 6.0 x ULN) if believed deterioration of renal function is suspected (as evidenced by changes in other markers of renal function, such as BUN, cystatin C, or calculated GFR based on cystatin C)	Discontinue ABEMACICLIB

General Guidance for Hematology Toxicity and Dose Modification

Hematologic toxicities including neutropenia, leukopenia, anemia, and thrombocytopenia have been observed in patients treated with abemaciclib, and causality has been established. Severe (Grade 3 and 4) neutropenia was observed in patients receiving abemaciclib. Patients should be monitored closely for signs of infection, anemia, and bleeding.

Anemia	First Occurrence:
- Grade 3 (Hgb <8.0 g/dL; <4.9 mmol/L; <80 g/L; transfusion	Interrupt until resolved to ≤ grade 2, then resume ABEMACICLIB at the current dose level
indicated)	Second Occurrence:
	Interrupt until resolution to ≤ grade 2, then resume ABEMACICLIB at one lower dose level
Anemia - Grade 4 (Life-threatening consequences; urgent intervention indicated)	Interrupt until resolution to ≤ grade 2, then resume ABEMACICLIB at one lower dose level

Patient requires administration of a blood cell growth factor	Suspend abemaciclib dose for at least 48 hours after the last dose of blood cell growth factor and until toxicity resolves to ≤Grade 2.
	Resume abemaciclib at next lower dose unless the dose was already reduced for the toxicity that led to the use of the growth factor.
Neutropenia	First Occurrence:
- Grade 3 (ANC < 1.0 - 0.5 x 10 ⁹ /L)	Interrupt until resolved to ≤ grade 2, then resume ABEMACICLIB at the current dose level
	Second Occurrence:
	Interrupt until resolution to ≤ grade 2, then resume ABEMACICLIB at one lower dose level
Neutropenia - Grade 4 (ANC < 0.5 x 10 ⁹ /L)	Interrupt until resolution to ≤ grade 2, then resume ABEMACICLIB at one lower dose level
31446 + (AIRC \ 0.5 X 10 /L)	
Patient requires administration of a blood cell growth factor	Suspend abemaciclib dose for at least 48 hours after the last dose of blood cell growth factor and until toxicity resolves to ≤Grade 2.
	Resume abemaciclib at next lower dose unless the dose was already reduced for the toxicity that led to the use of the growth factor.
Thrombocytopenia	First Occurrence:
- Grade 3 (<50-25 x 10 ⁹ /L PLT)	Interrupt until resolved to ≤ grade 2, then resume ABEMACICLIB at the current dose level
	Second Occurrence:
	Interrupt until resolution to ≤ grade 2, then resume ABEMACICLIB at one lower dose level
Thrombocytopenia - Grade 4 (PLT < 25 x 10 ⁹ /L)	Interrupt until resolved to ≤ grade 2, then resume ABEMACICLIB at one lower dose level
Patient requires administration of a blood cell growth factor	Suspend abemaciclib dose for at least 48 hours after the last dose of blood cell growth factor and until toxicity resolves to ≤Grade 2.
	Resume abemaciclib at next lower dose unless the dose was already reduced for the toxicity that led to the use of the growth factor.
	•

Gastrointestinal Disorders

Guidelines for Diarrhea Management

Clinical trial data indicates the majority of patients who receive abemaciclib will develop diarrhea. Our experience indicates early identification and intervention for the management of diarrhea has been helpful to patients.

At enrollment, patients should receive instructions on the prompt management of diarrhea. In the event of diarrhea, supportive care measures should be initiated as early as possible. These include the following:

- At the first sign of loose stools, the patient should initiate antidiarrheal therapy (e.g. loperamide) and notify the investigator for further instructions and appropriate follow up.
- Patients should also be encouraged to drink fluids (e.g., 8 to 10 glasses of clear liquids per day).
- Site personnel should assess response within 24 hours.

Diarrhea - Grade 2 (4-6 stools/day > pretx)	If diarrhea can be controlled with optimal anti-diarrheal treatment within 24 hours to either baseline or grade 1, continue ABEMACICLIB. If not, interrupt treatment until resolved to \leq grade 1, then resume ABEMACICLIB at the current dose (treating investigators may reduce by 1 dose level at their own discretion for first occurrence). If diarrhea persists or returns as \geq grade 2, then interrupt treatment until resolved to \leq grade 1, then resume ABEMACICLIB at one lower dose level.
Diarrhea - Grade 3 (7-9 stools/day > pretx) - Grade 4 (≥ 10 stools/day > pretx) (requires hospitalization)	If diarrhea can be controlled with optimal anti-diarrheal treatment within 24 hours to either baseline or grade 1, continue ABEMACICLIB. If not, for diarrhea \geq Grade 3 or requires hospitalization, interrupt treatment until resolved to \leq grade 1, then resume ABEMACICLIB at one lower dose level.

Respiratory, Thoracic, and Mediastinal Disorders

General Guidance for Interstitial lung disease (ILD)/Pneumonitis events

Interstitial lung disease (ILD) / pneumonitis has been identified as an adverse drug reaction for abemaciclib. Adverse events reported included events such as interstitial lung disease, pneumonitis, obliterative bronchiolitis, organizing pneumonia, pulmonary fibrosis. The majority of events were Grade 1 or Grade 2 with serious cases and fatal events reported.

Monitor for clinical symptoms or radiological changes indicative of ILD/pneumonitis and please ask patients to report any new or worsening pulmonary symptoms. Symptoms may include hypoxia, cough, dyspnea, or interstitial infliltrates on radiologic exams.; these symptoms should be investigated and treated as per local clinical practice and/or guidelines (including corticosteroids as appropriate). Infectious, neoplastic, and other causes for such symptoms should be excluded by means of appropriate investigations. Investigations may include imaging such as high resolution computer tomography (HRCT), broncheoalveolar lavage (BAL), and biopsy as clinically indicated (see also Table 7: refer to dose adjustment table for interstitial lung disease/pneumonitis).

Grade 1 or 2	Maintain treatment with ABEMACICLIB		
Persistent or recurrent Grade 2 toxicity that does not resolve with maximal supportive measures within 7 days to baseline or Grade 1	Interrupt until resolution to ≤ grade 1 or baseline, then resume ABEMACICLIB at one lower dose level		
Grade 3 or 4	Discontinue ABEMACICLIB		
Other unspecified RELATED adver	se events		
Other unspecified Grade 1 and 2 events considered at least possibly related to ABEMACICLIB	Maintain treatment with ABEMACICLIB		
Other unspecified persistent or recurrent Grade 2 events	Interrupt until resolution to ≤ grade 1 or baseline, then resume ABEMACICLIB at one lower dose level		

considered at least possibly related to ABEMACICLIB that dose not resolve with maximal supportive measures within 7 days to baseline or Grade 1	
Other unspecified Grade 3 or 4 events considered at least possibly related to ABEMACICLIB	Interrupt treatment until resolution to ≤ grade 1 or baseline, then resume ABEMACICLIB at one lower dose level. Continuation of ABEMACICLIB is permitted upon recovery to stable Grade 2 if the investigator and overall principal investigator ([name] [name]) agree that the event is not considered clinically significant.
Other unspecified UNRELATED ad	verse events
Other unspecified events of any grade considered unlikely to be related or not related to study drug.	Maintain treatment with ABEMACICLIB. Interruption of ABEMACICLIB is permitted at the treating investigator's discretion. It is recommended that the investigator consults with the overall principal investigator ([name] [name]) to determine that this is in the interest of the participant.

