5.2 Cohort 1—Surgery Arm

In Cohort 1, 15-20 eligible participants who require reoperation will be treated with abemaciclib for 10-14 days prior to surgery. The last dose should be on the day of surgery and taken 1-3 hours prior to surgery and tumor removal. Since participants in cohort 1 are undergoing PK testing, accurately recording the time of study drug administration on day of surgery and recording the time of tumor removal are especially important and required.

In general, pre-operative, operative, and post-operative evaluations will consist of standard clinical practice. Required evaluations and research samples are detailed in Section 10.

After surgery on study, cohort 1 participants will come off study treatment and pursue standard cancer treatments as per the treating physician's discretion. Participants who enrolled on the surgical cohort before the surgical cohort was converted into a Phase 0, who have already started post-surgical abemaciclib dosing, and are benefitting from post-surgical abemaciclib treatment may remain on abemaciclib at the discretion of their treating physician and the approval of the overall PI, [name]. These patients should instead follow the Study Calendar intended for Cohort 2 (nonsurgical) patients and their post-surgical C1D1 will represent C1D1 on the Cohort 2 study calendar.

Following registration, Cohort 1 pre-surgical Day 1 subjects should be evaluated for eligibility to treat based upon dose modification criteria outlined in Table 6.3 and not General Eligibility Criteria outlined here in Protocol Section 3; General Eligibility Criteria outlined here in Protocol Section 3 need only be met during screening for trial.

The goal is to have 15 eligible patients with adequate tissue for assessment of the primary objectives for this cohort. If sufficient tissue is not obtained for a patient enrolled in this cohort, the patient should continue treatment as originally intended and the clinical results reported. However, additional patients will be added to the cohort for the purpose of meeting the objectives related to tissue analysis. A maximum of 20 patients may be enrolled in this cohort. If the number of patients required to be replaced exceeds 5 consideration will be given to stopping enrollment to this cohort based on lack of feasibility.

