5.4 General Concomitant Medication and Supportive Care Guidelines

Participants must be instructed not to take any additional medications (including over-the-counter products) during the trial without prior consultation with the investigator. All medications taken from date of consent up to 30-day post drug study visit (as detailed in Section 10) should be recorded. If concomitant therapy must be added or changed, including over-the-counter medications or alternative therapies, the reason and name of the drug/therapy should be recorded.

In general, the use of any concomitant medication/therapies deemed necessary for the care of the participant are allowed, including drugs given prophylactically (e.g. antiemetics) with the following exceptions:

- 5.4.1 Abemaciclib is predominantly cleared by oxidative metabolism via CYP3A4. Clinical drug interaction studies with a CYP3A inhibitor and CYP3A inducer significantly altered the PK of abemaciclib and its circulating major metabolites.
 - Avoid concomitant use of CYP3A inducers and consider alternative agents.
 - Avoid concomitant use of strong CYP3A inhibitors (for example, voriconazole) and use caution with coadministered moderate (for example, ciprofloxacin) or weak (for example, ranitidine) CYP3A inhibitors. If coadministration with a strong CYP3A inhibitor is unavoidable, reduce the abemaciclib dose to 100 mg twice daily or, in the case of ketoconazole, reduce the abemaciclib dose to 50 mg twice daily. In patients who have had a dose reduction to 100 mg twice daily due to adverse reactions, further reduce the abemaciclib dose to 50 mg twice daily. Avoid grapefruit or grapefruit juice. If a CYP3A inhibitor is discontinued, increase the abemaciclib dose (after 3-5 half-lives of the inhibitor) to the dose that was used before starting the inhibitor.
- 5.4.2 Caution should be exercised when co-administering abemaciclib with narrow therapeutic drugs that are substrates for CYP1A2, CYP2B6, CYP2C8, CYP2C9, CYP2D6, or CYP3A. Participants receiving such medications must be monitored for potentiation of toxicity due to any individual concomitant medications, and may require dose titration or reduction of the drug substrate. Please refer to Appendix D for a list of drugs. Please note that this list may not be comprehensive.

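### The unqualified ban on dose re-escalation in Section 6.2.7 contradicts Section 5.4.1, which restores the dose after a CYP3A inhibitor is stopped

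*Combined protocol and SAP*

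**What the plan says.** Five places in the combined protocol and SAP bear on this point.

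- **Section 5.4.1 (concomitant medication), reduction.** "If coadministration with a strong CYP3A inhibitor is unavoidable, reduce the abemaciclib dose to 100 mg twice daily". With ketoconazole the dose goes to 50 mg twice daily. A separate rule covers earlier toxicity: "In patients who have had a dose reduction to 100 mg twice daily due to adverse reactions, further reduce the abemaciclib dose to 50 mg".
- **Section 5.4.1, restoration.** When the inhibitor is discontinued, the site is to "increase the abemaciclib dose (after 3-5 half-lives of the inhibitor) to the dose that was used before starting the inhibitor".
- **Section 6.2.7.** "Dose re-escalation is never permitted in this study". The sentence has no qualifier, exception or cross-reference.
- **Section 6, Table 6.0 footnote.** The optional increase to 200 mg at Cycle 2 is conditional: "If a patient has not required dose reduction(s) due to toxicity". Here the toxicity limit is written out.
- **Section 6.2.5.** "Participants cannot be treated below dose level -2", which is 50 mg every 12 hours. A participant already two levels down who needs a further reduction stops treatment, unless there has been benefit and the overall PI agrees to continuation.

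**The concern.** Both rules are current text and both govern the dose an individual participant takes. After an inhibitor-driven reduction they give opposite instructions.

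A site that obeys 6.2.7 keeps a participant who has shown no intolerance on a dose chosen to offset a drug that is no longer being taken. A site that obeys 5.4.1 breaks a rule worded as absolute. Under Appendix B, Section 3.9, departures from the approved protocol must be reported, and one without prospective IRB approval counts as a violation.

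There is also a knock-on effect on tolerability management. A participant left at 50 mg is at the dose floor, so the next toxicity that calls for a reduction ends treatment unless the exception in 6.2.5 is granted.

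**Working it through.** The plan gives no figure to reproduce here. The check sets the rules side by side and works out the dose each one produces.

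**Inputs**

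- Dose levels, each every 12 hours (Table 6.0): level 1 = 200 mg, level 0 = 150 mg (start), level -1 = 100 mg, level -2 = 50 mg.
- Dose with a strong inhibitor (5.4.1): 100 mg; 50 mg with ketoconazole; 50 mg if already at 100 mg for adverse reactions.
- After the inhibitor is stopped: return to the pre-inhibitor dose (5.4.1), or no increase (6.2.7 read literally).

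**Formula.** Shortfall = (pre-inhibitor dose - held dose) / pre-inhibitor dose.

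| Situation | Dose under 5.4.1 | Dose under 6.2.7 | Shortfall | Daily dose, 5.4.1 vs 6.2.7 |
|---|---|---|---|---|
| At 150 mg, strong inhibitor other than ketoconazole | 150 mg | 100 mg | (150-100)/150 = 33.3% | 300 vs 200 mg |
| At 150 mg, ketoconazole | 150 mg | 50 mg | (150-50)/150 = 66.7% | 300 vs 100 mg |
| At 100 mg for toxicity, then strong inhibitor | 100 mg | 50 mg | (100-50)/100 = 50% | 200 vs 100 mg |
| Already escalated to 200 mg, other strong inhibitor | 200 mg | 100 mg | (200-100)/200 = 50% | 400 vs 200 mg |
| Already escalated to 200 mg, ketoconazole | 200 mg | 50 mg | (200-50)/200 = 75% | 400 vs 100 mg |

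The last two rows need an earlier escalation, which is possible only from Cycle 2. The two rules give different doses in every row.

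**Reduction steps left.** This assumes that a reversed inhibitor-driven cut does not count toward the two-level limit in 6.2.5, which the text does not settle. From 150 mg with ketoconazole, a participant held at 50 mg (level -2) has 0 steps left; restored to 150 mg (level 0), 2 steps. For a participant at 100 mg for toxicity and cut to 50 mg for an inhibitor, it is 0 steps if held and 1 if restored.

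**Does other text resolve the conflict?** No.

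- No sentence makes 6.2.7 subject to 5.4.1, or the reverse.
- Neighbouring rules state their exceptions: 6.2.2 has a labelled one, and 6.2.5 and 6.2.6 allow continuation after contact with the overall PI. 6.2.7 has none.
- The Table 6.0 footnote counts only reductions for toxicity. A participant reduced in Cycle 1 solely for an inhibitor therefore stays eligible for 200 mg at Cycle 2, while 6.2.7 read literally forbids even a return to 150 mg.

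**Who can be affected.** Section 3.2 excludes participants on strong CYP3A inhibitors, with a 14-day washout. Appendix D marks strong inhibitors as prohibited, and 5.4.1 tolerates them only when unavoidable. Section 2.4 reports that Cohort 2 accrual is complete, with median PFS of 55 days. Under Section 5.2, new Cohort 1 participants take drug for 10-14 days before surgery and then stop. That leaves mainly any Cohort 2 participant still on drug and those Cohort 1 participants who started post-surgical dosing before the conversion to Phase 0 and "may remain on abemaciclib at the discretion of their treating physician and the approval of the overall PI". Neither number is given.

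**The case against.** The strongest reply is that context already supplies the limit. Section 6 opens with participants "unable to tolerate the protocol-specified dosing schedule, dose adjustments are permitted", and most of the items around 6.2.7 concern toxicity or adverse events. Section 5.4.1 is a complete instruction for one situation, and a specific rule normally governs its own case. On that reading only a qualifier is missing. This is very likely what was intended, but it shows what the sentence should say and does not change what it does say. An absolute rule that applies to the whole study gives a site no textual licence to increase the dose.

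The second reply is that reach may be close to nil: strong inhibitors are hard to encounter, few Cohort 2 participants can still be on drug, and the pre-surgical window barely fits an inhibitor's start, stop and washout. This stands. It limits the importance of the point but not its correctness.

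The third reply is that the loss of two reduction steps applies only to ketoconazole from 150 mg. That is right for a participant with no earlier toxicity. The other route to 50 mg involves someone already reduced for adverse reactions, who regains one step and has shown some intolerance.

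The last reply is that a one-sentence rewording leaves two matters open: toxicity that arises while the inhibitor is being taken, and whether inhibitor-driven cuts count toward the limit in 6.2.5. On the first, a cap at the toxicity-reduced level gives a clear, conservative answer in keeping with the existing ban. The second is a useful addition and does not undo the correction.

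**Conclusion.** The concern holds. Sections 5.4.1 and 6.2.7 cannot both be followed once a CYP3A inhibitor that prompted a reduction is stopped, and 6.2.7 is wrong as worded. From the starting dose, literal use of 6.2.7 costs the participant 33% of the dose, or 67% after ketoconazole, for a reason that no longer applies.

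This rests on reading 6.2.7 as written and on 5.4.1 being the intended handling of an interaction; its place in the more specific section supports the latter. The number of participants exposed is unknown and may be zero. Nothing in the PFS6 analysis, its success threshold or the sample size depends on it. It should be corrected because the contradiction is certain and the correction costs almost nothing while dosing is still allowed.

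**What to change.** Reword 6.2.7 along these lines: *After a reduction for toxicity, the dose may not be raised again. A reduction made only because of a CYP3A inhibitor is reversed as described in 5.4.1, back to the pre-inhibitor dose and never above a level set by a toxicity reduction.* Add a reference to 6.2.7 in 5.4.1.

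This keeps the safety purpose of the ban. A participant reduced to 100 mg for toxicity and then to 50 mg for an inhibitor returns to 100 mg and no higher. A participant reduced from 150 to 100 mg for an inhibitor and then to 50 mg for toxicity stays at 50 mg.

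The same amendment could state in 6.2.5 whether inhibitor-driven reductions count toward the two-level limit.

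The cost is one reworded sentence and one cross-reference, plus the optional clause in 6.2.5, with no effect on the analysis or sample size.
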